- Evaluate the proportion of patients achieving clinical response and biochemical response (fecal calprotectin [FC] and C-reactive protein [CRP]) at Weeks 12, 24, and 54.
- Measure improvement in patient-reported outcomes (PROs), including the urgency numeric scale (UNRS), at Weeks 12, 24, and 54.
- Assess mucosal and histological healing at Week 54 using endoscopy and biopsy.
- Evaluate changes in rectal and colonic wall thickness via ultrasound, if feasible[6].

Endpoints

Composite Endpoint:

Proportion of patients achieving deep remission at 54 ± 4 weeks, defined as: Mayo rectal bleeding subscore = 0, stool frequency subscore = 0, endoscopic subscore ≤ 1 .

Secondary Endpoints:

- Proportion of patients achieving clinical response at Weeks 12, 24, and 54, defined as
 a decrease from baseline in Mayo Clinic total score of ≥3 points and ≥30%, with a
 decrease in rectal bleeding subscore of ≥1 or an absolute rectal bleeding subscore of
 0 or 1.
- Change from baseline in PRO scores, including the urgency numeric scale (UNRS), at Weeks 12, 24, and 54.
- Proportion of patients achieving biochemical response (normalization or significant reduction in FC and CRP levels) at Weeks 12, 24, and 54.
- Safety outcomes: Incidence and severity of adverse events (AEs), serious adverse events (SAEs), and discontinuations due to AEs throughout the study.

Outcomes measurement

Primary Outcome Measures:

1. Clinical Remission at 24 and 54 ± 4 weeks

 \circ To assess the proportion of patients achieving clinical remission at 54 ± 4 weeks, defined as a modified Mayo score (MMS) with a rectal bleeding subscore of 0, stool frequency subscore of 0 or 1 with at least a 1-point reduction from baseline, and an endoscopic subscore of 0 or 1 (excluding friability).

Secondary Outcome Measures:

1. Endoscopic Remission at 54 ± 4 weeks

To determine the proportion of patients attaining endoscopic remission at 54 ± 4 weeks, defined as a Mayo endoscopic subscore of 0 or 1 (excluding friability) and UCEIS score.

2. Histologic Remission at 54 ± 4 weeks

o To evaluate histologic remission at 54 ± 4 weeks using the Nancy histological score. Remission is defined as a Nancy histological score of 0.

3. Symptomatic Remission at 12, 24 e 54 ± 4 weeks

To assess the proportion of patients achieving symptomatic remission at 12,
 24 e 54 ± 4 weeks, defined as a Mayo score with a rectal bleeding subscore of
 0 and a stool frequency subscore of 0 or 1 with at least a 1-point decrease

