 from baseline.

4. Endoscopic Response at 54 ± 4 weeks

 To evaluate the proportion of patients achieving endoscopic response at 54 ± 4 weeks, defined as at least a 1-point reduction from baseline in the Mayo endoscopic subscore.

5. Clinical Response at 12, 24 and 54 ± 4 weeks

 \circ To determine the proportion of patients achieving clinical response at 12, 24 e 54 \pm 4 weeks, defined as a decrease of at least 2 points and 30% from baseline in the 9-point MMS, with either a reduction of rectal bleeding subscore by at least 1 point or an absolute rectal bleeding subscore of 0 or 1.

6. Change in Fecal Calprotectin and C-Reactive protein from Baseline to 12, 24 e 54 ± 4 weeks

 \circ Biochemical response will be defined as either normalization (FC < 150 μg/g and CRP < 5 mg/L) or a ≥50% reduction from baseline values in patients with elevated biomarkers at study entry.

7. Change in Bowel Urgency Based on the Urgency NRS from Baseline to 12, 24 e 54 ± 4 weeks

 To evaluate changes in bowel urgency severity using the Urgency Numeric Rating Scale (NRS) at 12, 24 e 54 ± 4 weeks.

8. Comparing Effectiveness Across Different Treatment Lines by 54 ± 4 weeks

• To compare the efficacy of Etrasimod in achieving the primary study endpoint when used as a second, third, or fourth-line biological treatment.

9. Normalization of Bowel Wall Thickness (BWT) at 12, 24 e 54 ± 4 weeks (optional)

• To determine the proportion of patients exhibiting normalization of bowel wall thickness (BWT) on intestinal ultrasound (IUS), defined as a rectum ≤4.0 mm, sigmoid colon ≤4.0 mm, descending colon ≤3.0 mm, transverse colon ≤3.0 mm, and ascending colon ≤3.0 mm, at 12, 24 e 54 ± 4 weeks. This will be evaluated only in patients with increased BWT at baseline. [7,8]

10. Ultrasound Remission at 12, 24 e 54 ± 4 weeks (optional)

 To evaluate the proportion of patients achieving an intestinal ultrasound remission score of ≤6.2 based on the Milano Ultrasound Criteria (MUC) after 12, 24 e 54 ± 4 weeks of Etrasimod treatment. This will be evaluated only in patients with an MUC score >6.2 at baseline.

11. Deep Remission at 12, 24 e 54 ± 4 weeks

To assess the proportion of patients achieving deep remission at 12, 24 e 54 ± 4
weeks, defined as a rectal bleeding subscore of 0, a stool frequency subscore of 0,
and an eMayo score ≤1. [9]

12. Disease Clearance at 12, 24 e 54 ± 4 weeks

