• To evaluate the proportion of patients achieving disease clearance at 12, 24 e 54 \pm 4 weeks, defined as simultaneous attainment of deep remission (see above) and histologic remission (Nancy Histological Index = 0, indicating absence of significant inflammatory infiltrate)

13. Quality of Life Assessment

- To assess changes in health-related quality of life, measured using the IBD Disability Index (IBD-Disk) and the Functional Assessment of Chronic Illness Therapy–Fatigue (FACIT–Fatigue) questionnaire, 12, 24 e 54 ± 4 weeks.
- 14. Safety assessment through the 54 weeks, reporting side effects related to Etrasimod

Study Population

Inclusion Criteria:

- Adults aged ≥18 years with a confirmed diagnosis of UC for at least 6 months.
- Moderate-to-severe UC defined by a Mayo Clinic total score between 6 and 12 inclusive, with an endoscopic subscore ≥2.
- Inadequate response, loss of response, or intolerance to at least one prior biologic therapy (e.g., anti-TNF agents, vedolizumab, ustekinumab).

Exclusion Criteria:

- Diagnosis of Crohn's disease or indeterminate colitis.
- History of colectomy or anticipated need for colectomy during the study period.
- Presence of colonic dysplasia or malignancy.
- Active or latent tuberculosis not adequately treated.
- Serious uncontrolled medical conditions (e.g., severe infection, significant hepatic or renal impairment).
- Known hypersensitivity to Etrasimod or its excipients.

Intervention

Etrasimod Dosing Regimen:

- Induction Phase:
 - Etrasimod 2 mg administered orally once daily.

Maintenance Phase:

• Etrasimod 2 mg administered orally once daily up to Week 54.

Study Assessments and Visits

Baseline (Week 0):

- Comprehensive clinical assessment, including 9-point MMS.
- Endoscopic evaluation to assess mucosal appearance (endoscopic MAYO and UCEIS scores).
- Histological assessment via biopsy (Nancy score).
- Baseline PROs, including urgency numeric scale (UNRS).
- Laboratory tests: FC, CRP, complete blood count (CBC), liver and renal function tests.
- Collection of demographic and disease-specific data.
- Ultrasound evaluation of colonic and rectal wall thickness, if feasible (Milan Ultrasound Criteria).

Week 12, 24, 54 Assessments:

- Clinical response and remission assessment.
- Laboratory tests: FC, CRP.
- PRO assessments, including UNRS.
- Endoscopic and histological evaluation at Week 54.
- Safety monitoring.
- Ultrasound evaluation (Week 54, if feasible).

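### Clinical response, deep remission and disease clearance are listed at Weeks 12 and 24, but the endoscopy and histology they need are scheduled after baseline only at Week 54

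*Protocol*

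**What the plan says.** **Schedule (Protocol, Study Assessments and Visits).** Baseline includes "Endoscopic evaluation to assess mucosal appearance (endoscopic MAYO and UCEIS scores" and a biopsy for the Nancy score. The combined list for Weeks 12, 24 and 54 then has "Endoscopic and histological evaluation at Week 54" and "Ultrasound evaluation (Week 54, if feasible". The same list includes an assessment of clinical response and remission without restricting it to one visit.

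**Outcomes (Protocol, Endpoints and Outcomes measurement).**
- Clinical response is listed at Weeks 12, 24 and 54 under two definitions. Endpoints uses the Mayo total score (a fall of at least 3 points and 30%). Secondary Outcome Measures, item 5, uses "a decrease of at least 2 points and 30% from baseline in the 9-point MMS". Both add a rectal bleeding condition.
- Item 11 is "Deep Remission at 12, 24 e 54 ± 4 weeks" and requires an endoscopic Mayo subscore of at most 1.
- Item 12 is "Disease Clearance at 12, 24 e 54 ± 4 weeks" and requires deep remission plus a Nancy index of 0.
- The primary outcome measure is headed "Clinical Remission at 24 and 54 ± 4 weeks", but the sentence beneath it gives only 54 ± 4 weeks. It requires an endoscopic subscore of 0 or 1.
- Item 9 is "Normalization of Bowel Wall Thickness (BWT) at 12, 24 e 54 ± 4 weeks (optional". Item 10, ultrasound remission, is also optional and has the same time points.

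**Analysis (Protocol, Statistical analysis).** Repeated measures at Weeks 12, 24 and 54 go into GEE models. The sentence names no outcome.

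**The concern.** Three outcomes are listed at visits where one of their components is not measured. The protocol gives no interim endoscopy, no score without endoscopy for these outcomes, and no rule for the missing subscore. Centers and analysts would have to improvise: leave the values missing, reuse the baseline endoscopy, or count only patients endoscoped for clinical reasons. These choices give different proportions, and the last gives a selected sample. In an open-label, single-arm study, a response definition settled after the data are seen is open to selection. A statistical analysis plan cannot repair this alone, because it cannot supply examinations that the protocol does not schedule.

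**Working it through.** The protocol gives no figure to reproduce here. The check sets each outcome's components against the visit plan, then asks how far the missing component matters.

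**1. Components against schedule at Weeks 12 and 24**

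| Outcome | Listed at | Component not scheduled then | Strength of the conflict |
|---|---|---|---|
| Clinical response | 12, 24, 54 | Endoscopic subscore | Firm |
| Deep remission | 12, 24, 54 | Endoscopic subscore | Firm |
| Disease clearance | 12, 24, 54 | Endoscopic subscore and Nancy index | Firm |
| Clinical remission | 24 (heading only), 54 | Endoscopic subscore | Heading conflicts with its own definition |
| Bowel wall normalization, ultrasound remission | 12, 24, 54 | Ultrasound | Both optional |

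The firm conflict covers 3 outcomes × 2 visits = 6 outcome-by-visit results. The clinical remission heading adds 1, and the two optional ultrasound outcomes add 2 × 2 = 4.

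The restriction to Week 54 looks deliberate. It appears inside a list headed with all three visits, and the secondary objective on mucosal and histological healing names Week 54. Endoscopic remission, endoscopic response and histologic remission are also listed only at Week 54.

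**2. Deep remission and disease clearance**

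Both need rectal bleeding 0, stool frequency 0 and an endoscopic subscore of at most 1. A patient who misses a symptom criterion is a known failure. A patient who meets both could be a success or a failure, depending on the unseen subscore. So the scheduled data give only an upper bound: the proportion with bleeding 0 and stool frequency 0.

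**3. Clinical response on the 9-point MMS (item 5)**

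Inputs:
- Rectal bleeding, stool frequency and endoscopy are each scored 0 to 3.
- Baseline endoscopy is 2 or 3, from the inclusion criterion of at least 2.
- Baseline MMS is at least 4. This is an assumption, because the protocol sets entry on the Mayo total score.

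Rule: response if the fall is at least 2 points and at least 30% of baseline, and bleeding falls by at least 1 or ends at 0 or 1.

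Baseline patterns: 4 × 4 × 2 = 32. Removing those below 4 takes out 3 with endoscopy 2 and 1 with endoscopy 3, leaving 28. Each is combined with 4 × 4 = 16 follow-up symptom patterns: 28 × 16 = 448. For each pattern, the rule was applied with follow-up endoscopy set to 0, 1, 2 and 3.

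| Result without endoscopy | Patterns | Share |
|---|---|---|
| Response whatever the endoscopy | 69 | 15.4% |
| Non-response whatever the endoscopy | 220 | 49.1% |
| Depends on the endoscopy | 159 | 35.5% |

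The baseline assumption hardly matters. Entry at a Mayo total of 6 on a 12-point scale, with 3 points outside the MMS (12 − 9), allows a baseline MMS as low as 6 − 3 = 3. With a floor of 3 the undetermined share is 168 of 496 (33.9%). With a floor of 5 it is 134 of 368 (36.4%).

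Example: baseline 2 + 2 + 2 = 6; follow-up bleeding 1 and stool frequency 2. Bleeding has fallen by 1, so that condition is met. With follow-up endoscopy e, the fall is 6 − (3 + e) = 3 − e. The requirement is max(2, 0.30 × 6 = 1.8) = 2. The patient is a responder if e is 0 or 1 and a non-responder if e is 2 or 3.

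**The case against.** **Some data exist at the early visits.** Weeks 12 and 24 include a clinical assessment, and symptomatic remission (item 3) presupposes bleeding and stool frequency scores there. A reader might infer that these outcomes have no data at Weeks 12 and 24, or are missing for everyone. That goes too far: 289 of the 448 MMS patterns (69 + 220) are decided without endoscopy, and symptom failures are known. What stands is that the proportions as defined cannot be computed.

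**Remission need not be 0%.** A reader might infer that early remission would be 0%, because every patient enters with an endoscopic subscore of at least 2. That holds for deep remission, disease clearance and any Week 24 clinical remission, but only if baseline endoscopy is carried forward, and the protocol states no such rule. Symptomatic remission would be unaffected in any case.

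**Clinical remission at Week 24 may be a slip.** It appears only in a heading, and the definition beneath gives Week 54. This is an inconsistency to resolve, not proof of a planned Week 24 analysis.

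**The GEE sentence names no outcome.** It can be read as covering symptomatic remission, urgency, the biomarkers and the questionnaires, all of which are available. The protocol does not commit GEE to deep remission or clearance.

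**Ultrasound is optional.** It needs neither endoscopy nor histology, and the slip may be in the visit list as easily as in the outcome list. It is a separate, smaller mismatch.

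These points narrow the finding. None of them supplies the missing component for clinical response, deep remission or disease clearance.

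**Conclusion.** The point holds in a limited form. Clinical response, deep remission and disease clearance cannot be computed as defined at Weeks 12 and 24 from the scheduled data. For deep remission and clearance no success can be confirmed and only an upper bound is available. For clinical response on the MMS, about a third of possible score patterns are undetermined (159 of 448; 33.9% to 36.4% for baseline floors of 3 and 5).

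That share counts patterns equally and is not a forecast of the share of patients, which depends on how scores are distributed. It applies to item 5. It was not computed for the Mayo total score version under Endpoints, which has the same missing subscore.

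The clinical remission heading and the ultrasound time points are secondary inconsistencies. The primary endpoint, deep remission at Week 54, has its endoscopy scheduled and is unaffected. Clinical response at Weeks 12 and 24 is nevertheless a stated secondary objective, so the text should be corrected before data accrue.

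**What to change.** 1. Restrict clinical remission, deep remission and disease clearance to Week 54, and remove Week 24 from the clinical remission heading.
2. At Weeks 12 and 24, report symptomatic remission (item 3), urgency, fecal calprotectin and CRP, and a clinical response based only on rectal bleeding plus stool frequency. State its threshold before any data are seen, and align Endpoints with item 5. A partial Mayo score would suit less well, because it needs a global assessment that the visit list does not name.
3. State that baseline endoscopy is not carried forward.
4. State that the Week 12, 24 and 54 GEE models are run only on outcomes measured at all three visits.
5. Reconcile the ultrasound time points with the visit list, in whichever direction the sponsor intends.

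The cost is wording in the outcome list, the visit list and one paragraph of the analysis section, with no extra endoscopy. The downside is fewer early endpoints, and those removed could not have been computed as defined.

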Urgency Numeric Rating Scale (UNRS) Assessment:

- Urgency severity will be evaluated using the validated UNRS, with scores ranging from 0 (no urgency) to 10 (worst possible urgency).
- Improvement in UNRS scores will be analyzed at Weeks 12, 24, and 54, and correlated with clinical remission and mucosal healing.
- This assessment will provide insights into symptom control and quality of life improvements in Etrasimod-treated patients.

Safety Monitoring

- Adverse events will be recorded and graded according to the Common Terminology Criteria for Adverse Events (CTCAE) version 5.0.
- Immediate reporting of any serious adverse events to relevant regulatory bodies.

Sample Size Determination:

The required sample size for McNemar's test of paired proportions, based on the asymptotic approximation by Miettinen (1968), with a two-sided alpha level of 0.05, power of 0.8, probabilities of discordant pairs 0–1 and 1–0 equal to 0.35 and 0.10 respectively [10], and a drop-out rate of 5%, is 68 pairs. The McNemar test will be used to assess changes in paired proportions, particularly in the context of pre- and post-intervention comparisons of binary outcomes.

Data Collection

Statistical analysis

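### Deep remission, disease clearance and clinical response are set at Weeks 12 and 24, and clinical remission is headed Week 24, but the endoscopy and biopsy they need are scheduled after baseline only at Week 54

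*Protocol*

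**What the plan says.** **Schedule.** Study Assessments and Visits places endoscopy and biopsy at baseline. One block then covers Weeks 12, 24 and 54 together, and a separate bullet in it limits the invasive examinations: "Endoscopic and histological evaluation at Week 54". The secondary objectives agree: "Assess mucosal and histological healing at Week 54 using endoscopy and biopsy".

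**Outcomes with earlier time points** (Endpoints and Outcomes measurement):

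- Item 11 is headed "Deep Remission at 12, 24 e 54 ± 4 weeks". Besides bleeding and stool frequency subscores of zero, it requires "and an eMayo score ≤1".
- Item 12 is headed "Disease Clearance at 12, 24 e 54 ± 4 weeks". It requires deep remission plus a Nancy index of 0. In both items the text repeats the three visits given in the heading.
- Primary Outcome 1 is headed "Clinical Remission at 24 and 54 ± 4 weeks". The sentence beneath it names only the Week 54 window. The definition includes an endoscopic subscore no higher than 1.
- Clinical response is set at Weeks 12, 24 and 54 in two places: from the Mayo total score under Endpoints, and from the 9-point modified Mayo score (MMS) in item 5.

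**Outcomes that fit the schedule.** Endoscopic remission, histologic remission and endoscopic response (items 1, 2 and 4) are set at Week 54 only. Symptomatic remission (item 3) is set at all three visits and uses bleeding and stool frequency alone.

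**The concern.** An outcome with an endoscopic component cannot be classified as achieved at a visit where no endoscopy is done. The protocol gives no symptom-only or biomarker substitute for these composites and no rule for a missing endoscopic component. Whoever analyses Weeks 12 and 24 would have to improvise, and every available route misleads:

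- Excluding patients without an endoscopy leaves no denominator from scheduled data.
- Counting the missing component as failure, or carrying the baseline value forward, fixes the result in advance for deep remission and disease clearance.
- Dropping the endoscopic component reports a symptom score under the name of deep remission.
- Using only unscheduled endoscopies gives a self-selected group, not a proportion of the cohort.

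An analysis plan can choose among these routes, but it cannot supply examinations that the visit schedule does not collect.

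**Working it through.** The protocol states no figure on this point, so there is none to reproduce. The check sets each outcome's components against the schedule. The planned 68 pairs (Sample Size Determination) serve only as a denominator.

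**Step 1. Could another scheduled endoscopy serve Weeks 12 or 24?** If the ±4 weeks applies to every visit, the windows are 12 ± 4 = 8 to 16, 24 ± 4 = 20 to 28, and 54 ± 4 = 50 to 58 weeks. The scheduled endoscopies fall at Week 0 and in Weeks 50 to 58. Neither lies in an earlier window.

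**Step 2. Components against schedule.**

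| Outcome | Early visits listed | Needs endoscopy | Needs biopsy | Scheduled at those visits |
|---|---|---|---|---|
| Deep remission (item 11) | 12, 24 | yes | no | none |
| Disease clearance (item 12) | 12, 24 | yes | yes | none |
| Clinical remission (Primary Outcome 1) | 24, heading only | yes | no | none |
| Clinical response (Endpoints; item 5) | 12, 24 | yes, through the score | no | none |
| Symptomatic remission (item 3) | 12, 24 | no | no | not needed |

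For clinical response, the endoscopic component follows from the protocol's own use of the scores. Primary Outcome 1 expresses the MMS through bleeding, stool frequency and endoscopic subscores. The entry criterion pairs the Mayo total score with an endoscopic subscore.

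**Step 3. What two simple missing-data rules would give.** Entry requires a baseline endoscopic subscore of at least 2. Deep remission, disease clearance and clinical remission require at most 1.

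- Baseline carried forward: no patient can meet the endoscopic component, so the rate is 0/68 = 0% whatever the drug does.
- Missing counted as failure: also 0/68 = 0%.
- Missing excluded: 0 evaluable patients from scheduled examinations, so no proportion exists.

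Clinical response differs slightly. With the baseline subscore carried forward, endoscopy contributes a fall of exactly 0 points, so the whole required fall must come from the other components. The rate is then biased downwards but is not necessarily 0%. With missing counted as failure it is 0%.

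**Step 4. Week 54.** The Statistical analysis section names deep remission at Week 54 as the primary endpoint. Endoscopy is scheduled at that visit, so this result can be produced.

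**The case against.** The strongest reply is that the trial's main result is untouched, and that is correct. Deep remission at Week 54 is the primary objective, the composite endpoint and the primary endpoint of the analysis section, and its endoscopy is scheduled. Several stronger readings also go further than the protocol supports:

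- **That a primary time point is lost.** Week 24 appears only in the heading of Primary Outcome 1, while the operative sentence gives Week 54. This is an inconsistency to correct, not clear evidence of a planned Week 24 primary analysis.
- **That the early results will read 0%, or that the repeated-measures model will fail.** The 0% depends on a missing-data rule that the protocol does not state. The sentence on generalized estimating equations (GEE) names Weeks 12, 24 and 54 but not the outcomes, so it does not commit the plan to modelling deep remission or disease clearance this way.
- **That the urgency analysis is affected.** The text reads "Improvement in UNRS scores will be analyzed at Weeks 12, 24, and 54, and correlated with clinical remission and mucosal healing". It does not require remission to be measured at the same visit as urgency, and early urgency change can be related to Week 54 status.
- **That the general remission bullet for Weeks 12, 24 and 54 implies earlier endoscopy.** This would defend the plan, but a separate bullet in the same list confines endoscopy and histology to Week 54.

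The reply limits the reach of the point. It does not remove the conflict between items 5, 11 and 12 and the schedule.

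**Conclusion.** The conflict is on the face of the protocol and needs no outside fact. Three secondary outcomes (deep remission, disease clearance and clinical response) are each listed at two visits where their endoscopic component is not collected. Disease clearance also lacks its biopsy there. Clinical remission has the same problem at Week 24, in its heading only. At those visits the scheduled data give 0 evaluable patients of 68 for deep remission and disease clearance, and likewise for clinical remission at Week 24. Clinical response cannot be scored as defined at either visit.

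This assumes that the visit schedule is complete as printed. Unscheduled endoscopies could add values for some patients, but not a valid cohort proportion. The Week 54 results, including the primary endpoint, stand.

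**What to change.** Reconcile the time points in Endpoints and Outcomes measurement with Study Assessments and Visits. Which examinations to perform, and when, is for the sponsor to decide. With the schedule as it stands:

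1. In items 11 and 12, remove Weeks 12 and 24 from both heading and text.
2. In Primary Outcome 1, remove Week 24 from the heading so that it matches its text.
3. For clinical response, under Endpoints and in item 5, either set it at Week 54 only or define it at Weeks 12 and 24 from the stool frequency and rectal bleeding subscores. An early version needs its own prespecified threshold and a distinct name, because the present thresholds belong to scores that include endoscopy.
4. Name symptomatic remission (item 3) as the early remission measure.
5. State that the repeated-measures GEE applies only to outcomes measured at all three visits, such as symptomatic remission, biochemical response and the urgency score.

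The cost is protocol wording. No scheduled data are lost, because the results removed have no scheduled examination behind them.

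### The 68 pairs do not follow from the stated inputs, which give 52 pairs, or 55 with 5% drop-out; the mismatch is conservative but should be corrected

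*Protocol*

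**What the plan says.** The Sample Size Determination section of the protocol gives a complete recipe. The calculation is introduced as "The required sample size for McNemar's test of paired proportions", and the method is the large-sample approximation of Miettinen (1968). The inputs are "with a two-sided alpha level of 0.05, power of 0.8, probabilities of discordant pairs 0–1 and 1–0 equal to 0.35 and 0.10 respectively". The result follows directly: "and a drop-out rate of 5%, is 68 pairs".

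The section gives no figure before drop-out and mentions neither a continuity correction nor an exact test. The Statistical analysis section says that McNemar's test will compare paired proportions, with remission status at baseline against Week 54 as its example. It does not say which version of the test (asymptotic, continuity-corrected or exact) will be used.

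**The concern.** Because every input and the method are printed, the result can be checked without any outside figure and without anything that might sit in a separate analysis plan. It does not come out at 68.

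This is the protocol's only justification of its size. If power, drop-out, a discordant probability or the method is not what was actually used, the reader cannot tell what the trial was designed to detect or with what power. An ethics committee or journal reviewer who repeats the calculation will find the same gap.

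**Working it through.** **Inputs, all from Sample Size Determination.** p01 = 0.35 and p10 = 0.10, so the discordant total is ψ = 0.45 and the difference is d = 0.25. Two-sided alpha 0.05 gives z = 1.960. Power 0.80 gives z = 0.8416. Drop-out is 5%.

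**Formula (Miettinen asymptotic).**

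n = [z(1−α/2)·ψ + z(power)·√(ψ² − d²(3+ψ)/4)]² / (ψ·d²)

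- Square root: √(0.2025 − 0.0625 × 3.45/4) = √0.14859 = 0.3855
- Denominator: 0.45 × 0.0625 = 0.028125

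**Attempt to reproduce 68 with the stated inputs.**

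- Numerator: (1.960 × 0.45 + 0.8416 × 0.3855)² = (0.8820 + 0.3244)² = 1.4554
- n = 1.4554 / 0.028125 = 51.75, so 52 pairs
- With drop-out: 52/0.95 = 54.7, so 55. Multiplying by 1.05 instead gives 54.6, also 55.
- Gap: 68 − 55 = 13 pairs, and 13/55 = 24%

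**The same formula at 90% power** (z = 1.2816).

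- (0.8820 + 0.4940)² / 0.028125 = 67.32, so 68 pairs before drop-out
- With drop-out: 68/0.95 = 71.6, so 72

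**Other routes at 80% power, two-sided.**

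| Method | Pairs | With 5% drop-out |
|---|---|---|
| Miettinen (the named method) | 52 | 55 |
| Conditional on discordant pairs | 51 | 54 |
| Connor (unconditional normal) | 55 | 58 |
| Simple ψ/d² formula | 57 | 60 |
| Miettinen with continuity correction | 60 | 64 |
| Exact McNemar, enumerated | 60 | 64 |
| Connor with continuity correction | 62 | 66 |
| Simple formula with continuity correction | 65 | 69 |

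None gives 68. The two that come close are not the method named.

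**Sensitivity to the discordant probabilities (Miettinen, 80% power).**

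- Rounding: 0.345 and 0.105 give 56.6, so 57 pairs, and 57/0.95 = 60. Rounding of the printed values does not explain 68.
- Mis-statement: 0.35 and 0.12 give 65.2, and 65.2/0.95 = 68.6. This is near 68 but not equal to it.

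**Power that 68 enrolled actually provide.** 68 × 0.95 = 64.6, so about 65 evaluable pairs. With p01 = 0.35 and p10 = 0.10:

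| Evaluable pairs | Miettinen formula | Asymptotic test, enumerated | Exact test, enumerated |
|---|---|---|---|
| 64 | 0.883 | 0.884 | 0.830 |
| 65 | 0.889 | 0.889 | 0.836 |
| 68 | 0.903 | 0.902 | 0.855 |

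**The case against.** The strongest reply is that nothing is put at risk. The printed number exceeds the requirement under the named method (55), and it still exceeds the 64 needed with the exact test. After the planned loss, power is 84% to 89% against a stated target of 80%. If an exact or continuity-corrected test is the one intended, the excess over Miettinen with continuity correction, or over the exact test, is 68 − 64 = 4 pairs rather than 13. All of this stands, and it is why the point is a matter of reproducibility and not of validity. It does not remove the mismatch, because the protocol names one formula and that formula does not return 68.

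A reader might also infer that the calculation was run at 90% power and that the drop-out allowance was forgotten. The exact match at 67.32 makes this tempting, but the protocol never mentions 90% power. Nor can it be said that either the power or the drop-out must be the faulty input. A 1–0 probability of 0.12 comes to 68.6 after drop-out, and two continuity-corrected formulas give 66 and 69, on either side of 68. The documents show that the inputs and the result disagree; they do not show which one is wrong.

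**Conclusion.** The point holds as a should-fix correction. Under the method and inputs printed in the protocol, the requirement is 52 pairs, or 55 with 5% drop-out, and 68 is 13 pairs (24%) above that. The agreement of 68 with the 90%-power figure before drop-out is consistent with a mis-stated power, but is not established.

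The documents do not support reading this as an underpowered trial. On the protocol's own assumptions the stated 80% is exceeded, at about 89% (asymptotic) or 84% (exact) with 65 evaluable pairs. Those figures take the discordant probabilities of 0.35 and 0.10 and the 5% drop-out as given. Whether these probabilities are realistic for the endpoint is a separate question that does not affect this arithmetic.

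**What to change.** Keep 68 and restate the paragraph so that power, drop-out and number agree while all stated inputs remain. For example: by the Miettinen (1968) approximation, 80% power needs 52 pairs, or 55 with 5% drop-out; 68 patients will be enrolled, and the roughly 65 evaluable give about 89% power (about 84% with the exact McNemar test).

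If the sponsor's records show that an input was mis-stated, correct that input and give the figure before and after drop-out. If 90% power after 5% drop-out was intended, the formula gives 72, so an enrolment of 68 should be described as giving about 89%. Relabelling 68 as 90% power and deleting the drop-out allowance is not a good repair: it removes a stated assumption, and a 5% loss would bring power below 90%.

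The cost is one paragraph of protocol wording, with no change in enrolment if 68 is kept.
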